16.3 Exercise

The interventions encourage patients to increase their level of resistance exercise, and light / moderate cardiovascular exercise in a carefully designed staged programme which presents a minimal risk of fractures, cardiovascular morbidity and other complications from breast cancer, e.g. cording or lymphoedema. The programme will be advised and supervised by experienced physiotherapists / cancer exercise specialist based on a rigorous assessment of their medical history and site of metastases, and current activity and energy levels and reviewed 3 weekly (Appendix 1). Any cardiovascular, musculoskeletal or arm problems identified during the trial will be referred to appropriate care pathways for assessment and treatment.

16.4 Serum blood tests

Fasting glucose and insulin will be assessed where possible in all participants attending baseline appointment either at MFT or their recruiting centre, and repeated at the start of cycle 3 or 4 for patients on sub-study 1 only. Glucose results will be fed back to the patient's oncologist during the study if outside of the normal range. Other blood test results will not be available until after the end of the study so there are no plans to feed these back to the medical team. Baseline and sub study blood samples will only be taken in centres which have -80°C storage facilities or if the samples can be transferred to MFT or another centre with -80°C storage facilities within an acceptable time frame.

Phlebotomy will be undertaken on the non-operated arm wherever possible to minimise the risk of lymphoedema. The study is designed so participants will have their trial blood samples collected at the time of routine chemotherapy blood tests wherever possible to minimise venepuncture.

16.5 Other Identified problems

The ongoing communication with trial participants during treatment means other psychosocial or medical issues will be raised and communicated to the trial team. The trial team will refer patients to appropriate services for further assessment, treatment or psychosocial support. We will be assessing anxiety and depression every three cycles during the trial using the hospital anxiety and depression scale. Patients who score > 11 are likely to have clinical depression or anxiety and will be referred for further support with their permission (e.g. referred to their breast care nurse, who may subsequently refer to psychological services in the hospital or in the community). Scores of 8-10 are borderline and referral will be made where considered necessary.

Any potential toxicity or adverse effects of IER will be assessed and acted upon three weekly by the research dietetic and / or clinical team.

We will have a data monitoring committee to independently assess recruitment, drop out and any adverse effects of the intervention.

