5.2 Secondary objectives

- 1. Self-reported toxicity according to the Common Terminology Criteria for Adverse Events version 4 (CTCAE v4)
- 2. Taxane neuropathy assessed with the VibraTip (McCallan Medical Ltd, Northamptonshire)
- 3. Abdominal muscle and fat cross sectional areas at the L3 level in CT scans.
- 4. Quality of life & fatigue using the FACT-B, FACT-ES (74), FACT-F (75) and FACT-BP (78) for bone pain, hospital anxiety and depression scale (76) in all patients and also: - FACT-taxane scale for patients receiving taxanes (77)
- 5. Muscle strength in the lower and upper limb. Lower limb strength from five repetition sit to stand test (FRSTST) (79). Upper limb strength assessed with hand grip dynamometry (80)
- 6. Fidelity of the interventions. Self -reported dietary intake (7 day food diary or diet history over the phone) and resistance exercise
- 7. Changes in concomitant medication
- 8. Change in blood protein biomarkers (proteomics) (Sub study 1)
- 9. Change in insulin resistance with HOMA from fasting insulin and glucose (81) (Sub study 1)
- 10. Time to Treatment Failure (TTF), i.e. the time from randomisation to disease progression, death or discontinuation of therapy due to toxicity
- 11. Objective response and clinical benefit rate (objective response plus stable disease for ≥6 months) between treatment groups
- 12. Overall survival

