Chemotherapy toxicity will be managed according to standard protocols within the Christie NHS trust and the other hospitals. All patients will have access to the 24 hour Christie chemotherapy hot line or local hot line for advice as to the management of toxicity, as well as their breast care nurse and the research nurses.

As the *a priori* aim of the study is for participants on the diet arm to lose weight, a loss of greater than 10% body weight may be seen more frequently on the intervention arm than the control group. In this case, if grade ≥ 2 toxicity has been observed within the last 2 cycles before the weight loss reached 10% or more, a dose reduction should be performed by recalculating the body surface area with the most recent weight. If no grade ≥ 2 toxicity is observed then no dose recalculation should be performed. If therapy is continued in this a manner and grade ≥ 2 toxicity develops subsequently then the recalculation should be performed on the most recent weight, not the one first observed to be <10% from baseline.

A change of chemotherapy regimen is not permitted prior to disease progression. This includes a switch from paclitaxel to 'maintenance' capecitabine which is specifically prohibited. A patient who has an allergic reaction to the first or second dose of weekly paclitaxel, who has not been treated previously with capecitabine, may change to capecitabine if, in the opinion of the treating clinician, this is an appropriate therapeutic option. HER2 targeted agents may be stopped during the study and the patient continue with chemotherapy. The date of stopping the HER2 targeted agent will be recorded.

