The following 2 assessments will be assessed at baseline, at the start of cycle 3, and then every 3 cycles thereafter whilst patients remain in the trial i¹.

If cycles are delayed these assessments will be pushed back to coincide with day 1 of each chemotherapy cycle.

4. Quality of life fatigue, anxiety and depression

These will be estimated using the FACT-B, FACT-ES (74), FACT-F (75), FACT-BP for bone pain (78), and HAD scales (76) in all patients. The FACT-Taxane scale for patients receiving taxanes. Questionnaires will be completed by patients when they attend their chemotherapy unit (77).

5. Muscle strength.

Lower limb strength will be assessed from five repetition sit to stand test (FRSTST), normalised by weight (79) (Appendix 3). Arm muscular strength will be assessed using hand grip dynamometer. Both tests will be assessed at baseline, and at cycle 3 and every three cycles thereafter during the study by the B-AHEAD 3 study team or research nurses in the recruiting centres, who have been trained to undertake assessments according to the trial standard operating procedure (Appendix 3).

- 6. Fidelity of the interventions. Adherence to the diet and exercise interventions
- The intervention group will be asked to record compliance to the IER diet each week during the study using a specially designed self-monitoring diary. They will be asked to record whether they have managed to undertake two, one or no restricted days that week. Compliance to the intervention will be checked and recorded as part of the three weekly calls from their B-AHEAD 3 advisor.
- Both groups will be asked to record compliance with the resistance exercise in a special trial diary and the number of sessions achieved each week for the first 18 weeks of chemotherapy only. This diary will ask patients to record pain pre and post as assessed by Cormie et al (65). The diet and exercise diaries will monitor fidelity with the interventions and also act as a behavioural tool to increase compliance and a record of any problems encountered when they try to follow an exercise programme.
- We will record receipt of the three weekly phone calls from the trial dietitian and physiotherapist / cancer exercise specialist in the intervention group and from the physiotherapist / cancer exercise specialist in the exercise only group, which are part of the diet and exercise interventions.

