10.1 Sample size and power calculations

The sample size was calculated for a phase II screening design, based on a primary outcome of progression free survival, with a time-to-event hazard ratio of 0.65, and with 90% power and a one-sided significance of 20%. Assuming that the estimated PFS in the control arm is 5.4 months, and that we will have a 15 month accrual period and a 15 month follow-up, then a total of 98 events will be required overall. This corresponds to 114 patients required in all, allowing for a 15% drop out we will need to recruit 134 patients overall. The sample size is for a randomised phase II screening design where a randomised phase III is planned in the future. This approach is approved by the Cancer Research UK trials organisation (CTAAC) (73).

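### The HADS referral rule in section 16.5 leaves out a score of exactly 11, although 10 and 12 both prompt action

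*Protocol*

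**What the plan says.** Section 16.5 (Other Identified problems) sets out when and how distress is to be acted on. The instrument and schedule come first: "We will be assessing anxiety and depression every three cycles during the trial using the hospital anxiety and depression scale". The upper rule follows: "Patients who score > 11 are likely to have clinical depression or anxiety and will be referred for further support with their permission". The lower rule is: "Scores of 8-10 are borderline and referral will be made where considered necessary".

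The same section also has a general undertaking about problems that come to light through contact with participants: "The trial team will refer patients to appropriate services for further assessment, treatment or psychosocial support". It mentions no score.

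The scale appears in three other places. Section 5.2 lists it as a secondary measure ("hospital anxiety and depression scale (76) in all patients"). Section 8.1.2 repeats this ("and HAD scales (76) in all patients") and schedules it at baseline, at the start of cycle 3 and every three cycles after that. Appendix 7 lists it in the schedule of assessments. None of the three gives a cut-off.

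**The concern.** The two rules are evidently meant to form one ladder: discretionary referral for borderline scores, then referral for scores above them. As written, a rung is missing. The borderline band stops at 10 and the referral band starts strictly above 11, so the score between them has no rule.

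The result runs against the purpose of the ladder, because the written response to 11 is weaker than the response to 10. No reason is given for that order, and it is hard to think of one. At stake is whether a woman with advanced cancer whose score lies just above the borderline range is offered support. Questionnaires are completed in the chemotherapy units, and section 6.3 names 11 recruiting units at the start, with more possible. Across that many sites and staff, a written threshold is what keeps the response consistent.

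**Working it through.** The protocol states no figure to reproduce here. The check is to apply the two written rules to each possible score.

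**Inputs, both from section 16.5**

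- Referral band: score > 11, which on whole numbers means 12 and above.
- Borderline band: 8 to 10 inclusive.

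**Assumptions**

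- Scores are whole numbers, as the bands themselves imply.
- The scores checked ran from 0 to 21. The upper end is an assumption and does not affect the result. Section 16.5 does not say whether the score is a subscale or a total, and the gap at 11 exists either way.

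**Result**

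| Score | Rule as written (> 11) | With ≥ 11 |
|---|---|---|
| 0–7 | none | none |
| 8–10 | discretionary referral | discretionary referral |
| 11 | **none** | referral |
| 12 and above | referral | referral |

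As written, the scores of 8 or more that have an action are {8, 9, 10} and {12, 13, …}. The set left out is {11}. Among the five values from 8 to 12, which span the join between the bands, that is 1 of 5.

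With ≥ 11 the bands are {8, 9, 10} and {11, 12, …}. No value of 8 or more is left out, none falls in both bands, and 11 is the only score whose action changes.

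**Does anything else in the protocol cover 11?** Sections 5.2 and 8.1.2 and Appendix 7 name the scale without a threshold. The general referral sentence in section 16.5 permits help at any score, but a score does not trigger it. It softens the gap without closing it.

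**Could a sign have been lost in reading the PDF?** The ≥ sign comes through elsewhere in the same text, for example in the grade ≥ 2 toxicity rule of section 6.4. A loss at this one place is unlikely, though it cannot be ruled out.

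**Reach.** Every participant completes the scale, and section 10.1 says "we will need to recruit 134 patients overall". So 134 is the number of women to whom the rule applies, not the number expected to score 11. With no score distribution in the protocol, the latter cannot be calculated.

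**The case against.** The strongest reply is that this is proofreading. A sensible clinician who may refer at 10 and must refer at 12 would not ignore 11. The general undertaking in section 16.5 gives all the authority needed, and section 7.3.2 provides roughly three-weekly contact in both arms, so distress has other ways of coming to light. Much of this stands, and it is why the point is small. It does not remove the defect. The general undertaking is not tied to the questionnaire, the calls can be made less frequent at the participant's request, and a threshold rule should not rely on staff correcting it as they apply it.

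A second reply is that the protocol does not settle which repair was intended. Widening the borderline band to 8–11 would also close the gap. That is correct, and it is why the clinical leads should confirm the change. Reading the sign as ≥ 11 is the simplest repair, because the borderline band already ends at 10, and it is the more protective of the two.

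A third reply is that the sign may be correct in the source file. The possibility remains. If so, the point falls away once the original is checked.

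**Conclusion.** The concern holds. As the protocol reads, a HADS score of exactly 11 prompts no score-based action, while 10 prompts discretionary referral and 12 prompts referral. It is the only value of 8 or more left out. The conclusion rests on whole-number scoring and on the sign being as shown. That ≥ 11 was intended is an inference, though a likely one.

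The weight is low. This is an operational safety threshold that gives a perverse answer if followed literally. It should be corrected, but it does not touch progression-free survival, the sample size or any planned comparison.

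**What to change.** In section 16.5, change > 11 to ≥ 11, after the clinical leads confirm that this is the intended cut-off. If they meant 11 to be borderline, extend that band to 8–11 instead and leave the upper rule alone. Either way, every score of 8 or more then falls in exactly one band.

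The preferred change is one character. Its running cost is the referrals offered to women who score exactly 11. Their number cannot be estimated from the protocol, and each referral is made only with the patient's permission.

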16.6 Generic Risk Assessment

Hazards to patients, study and organisation have been perfomed for the B-AHEAD 3 trial and have been considered low risk.

17. Predicted/possible deviations from the protocol and adverse events

The following is a list of possible/predicted deviations from the protocol and adverse events that would not require reporting to the sponsor or ethics committee:

Deviation / adverse event	Action
The participant does not receive chemotherapy once randomised	Participant is withdrawn from the study
Chemotherapy regimen is not given according to initial schedule, e.g. if one or more cycles are delayed for medical reasons	Dates of chemotherapy cycles are documented in participant's study file. Participant remains on study.
Research blood samples cannot be taken	See Blood Sampling SOP (Appendix 6). Participant is encouraged to stay on study.
Participant does not (fully) complete required food diaries	Participant is encouraged to remain on study. Food diary checked through with participant and more detail added if possible. Participant is encouraged to complete next food diary fully, if applicable. A diet history can be taken by BAHEAD 3 dietitians to describe the normal dietary intake.
Participant cannot adhere to or does not wish to adhere to allocated diet and/or exercise plan	Participant will be encouraged to remain on study as they are providing very useful information to the study team. They will be encouraged to stick to their allocated diet/exercise plan as best as they can. Researcher will document reported adherence and reasons for not following allocated diet/exercise plan in participant's study file. Diet/exercise plan will be adapted to patient's requirements if possible and adaptations will be recorded.
One or more chemotherapy treatments are delayed and toxicity scales cannot be completed for last 3 weeks.	Scales to be completed at next chemotherapy treatment and participant encouraged to give answers based on how they were feeling in the three weeks after last chemotherapy.
Participant would prefer advice over phone rather than prolong study visit	Diet advice can be given over the phone instead of during the baseline appointment at the Prevent Breast Cancer Research Unit as planned. Exercise advice can be given using Skype (or similar application). If Skype is not possible, exercise advice can be delivered over the phone if the physiotherapist is happy that this is appropriate for the individual patient. Following such a consultation, written targets will be posted to participant.
Participant does not have access to Skype for the 3 week resistance exercise review and cannot / is not willing to come in for a face-to-face assessment.	In depth phone consultation with BAHEAD 3 physiotherapist / exercise specialist. If still concerned may need to arrange face to face review.

The full complement of blood sample bottles cannot be filled	See Blood Sampling SOP (Appendix 6). As many as possible are filled. Outcome documented in participant's study file.
Pregnancy during study	In the unlikely event of a pregnancy occurring during the study, the participant will be withdrawn from the study. Outcome documented in participant's study file. Pregnancies will not be tracked as part of the study.
Hospital clinician / GP prescribes additional medication (e.g. for nausea) during study period	Medication, date started and duration to be documented in participant's study file. This information will also be collected at each cycle by the research nurses. Also document if the patient has given additional diet/lifestyle advice (e.g. for nausea).
Unable to call participant every three weeks, or partipant requests calls at a different frequency	If consistently struggling to get a participant on the phone, ask them the next time you get them the frequency that they'd like to be called. If a participant requests less frequent calls the study team will document this and aim to adhere to their request.

All protocol deviations and adverse events listed above and other minor deviations not listed will be documented in participant's study file stating the event and action.

Reporting of key adverse events (see CRF) will follow the flow chart in Appendix 8 and data for all SAEs will reviewed by the DMC.

As there are many common side effects associated with delivering chemotherapy to women with advanced breast cancer, unrelated to the delivery of a diet and exercise programme, certain SAEs do not require reporting. These are:

Appendix 1: Resistance exercise programme

Information to be provided to the trial physiotherapist prior to the baseline appointment so programme can be planned prior their visit:

- Information to be provided by the referring oncology team:
 - What is the patient's performance status? Either 0 or 1.
 - Date of latest CT scan and what the scan shows, e.g. hepatomegaly, pleural effusion, ascites.
 - Recent scans and reports which show site of metastases.
 - o Location of any metastases, including bone metastases.
 - Do the metastases hinder the patients movement or mobility?
 - Pain in bone metastases?
 - What treatment has previously been given for metastases eg. XRT, denusamab, bisphosphonates, steroids, etc.
 - When was this treatment completed?
 - What general medication is the patient receiving now?
 - Any previous breast surgery or radiotherapy?
 - Does the patient have a Hickman line or peripherally inserted central catheter (PICC) line in situ?
 - Any co-morbidities and other relevant past medical history affecting the patient's ability to exercise, e.g. presence of abdominal ascites, breathlessness, balance impairment, osteoarthritis, arthropathy, risk of fracture due to osteoporosis, cardiac e.g. arrhythmias lymphoedema etc
 - Any other comments.
- Information to be provided by the patient:
 - Current level of activity and mobility i.e. how far can they walk.
 - What limits them, e.g. fatigue, breathlessness, arthritis, pain etc.
 - What is their upper body strength and any limitations, e.g. contraindications to exercise.
 - Any areas of weakness they might be concerned about.

Assessments undertaken at baseline appointment to tailor programme (physiotherapist at MFT or research nurse in recruiting centre with input from MFT physiotherapist).

- Fatigue FACT F, FACT BP, FACT- Taxane
- Pain scale at rest and after activity using a 10 point visual analogue score
- Tinetti assessment tool for balance (94) (Appendix 2)
- Range of movement for upper limb, lower limb and trunk
- Five times sit to stand test (FTSTST) for lower limb strength
- Hand grip strength for upper limb strength
- Pain vas before and after undertaking basic resistance exercise programme

Examples of resisted exercises for the upper limbs

The number of repetitions or weight can be altered to suit the patients ability/performance status:

- Double arm press-ups against the wall in standing
- Single arms press-ups against the wall in standing
- Biceps arm curls with weight in standing or sitting
- Biceps arm curls followed by shoulder flexion with weight in standing or sitting
- Shoulder abduction to the ceiling with elbow in extension with weight
- Shoulder abduction with the elbow flexed with or without weight
- Shoulder circumduction backwards with or without weight
- Shoulder circumduction forwards
- Shoulder presses (ie using pectoralis major/minor)adduction and abduction with elbows and shoulders flexed to 90 degrees

• Shoulder extension against the wall

Examples of resisted exercises for the lower limbs

- Sitting to standing without use of hands
- Half squats holding onto the back of a chair
- Step up and down off a step
- Flex the knee to the chest in standing
- Abduct straight leg in standing
- Etc

Examples of trunk exercises

- Side flexion to both sides with a weight in standing
- Trunk rotation with weight to both sides
- Stomach crunches in supine
- Stomach crunches diagonal on supine

TINETTI BALANCE ASSESSMENT TOOL

PATIENT'S NAME _____ DOB _____

BALANCE SECTION

Patient is seated in hard, armless chair;

	Date			
Sitting Balance	Leans or slides in chair	= 0		
	Steady, safe	= 1		
Rises from chair	Unable to without help	= 0		
	Able, uses arms to help	= 1		
	Able without use of arms	= 2		
Attempts to rise	Unable to without help	= 0		
	Able, requires > 1 attempt	= 1		
	Able to rise, 1 attempt	= 2		
Immediate standing	Unsteady (staggers, moves feet, trunk sway)	= 0		
Balance (first 5 seconds)	Steady but uses walker or other support	= 1		
	Steady without walker or other support	= 2		
Standing balance	Unsteady	= 0		
_	Steady but wide stance and uses support	= 1		
	Narrow stance without support	= 2		
Nudged	Begins to fall	= 0		
	Staggers, grabs, catches self	= 1		
	Steady	= 2		
Eyes closed	Unsteady	= 0		
	Steady	= 1		
Turning 360 degrees	Discontinuous steps	= 0		
	Continuous	= 1		
	Unsteady (grabs, staggers)	= 0		
	Steady	= 1		
Sitting down	Unsafe (misjudged distance, falls into chair)	= 0		
	Uses arms or not a smooth motion	= 1		
	Safe, smooth motion	= 2		
	Balance score		/16	/16

РТО

GAIT SECTION

	Date			
Indication of gait	Any hesitancy or multiple attempts	= 0		
(Immediately after told	No hesitancy = 1			
to 'go'.)				
Step length and height	Step to	= 0		
	Step through R	= 1		
	Step through L	= 1		
Foot clearance	Foot drop	= 0		
	L foot clears floor	= 1		
	R foot clears floor	= 1		
Step symmetry	Right and left step length not equal	= 0		
	Right and left step length appear equal	= 1		
Step continuity	Stopping or discontinuity between steps	= 0		
	Steps appear continuous	= 1		
Path	Marked deviation	= 0		
	Mild/moderate deviation or uses w. aid	= 1		
	Straight without w. aid	= 2		
Trunk	Marked sway or uses w. aid	= 0		
	No sway but flex. knees or back or			
	uses arms for stability	= 1		
	No sway, flex., use of arms or w. aid	= 2		
Walking time	Heels apart = 0	= 0		
	Heels almost touching while walking	= 1		
	Gait sco	re	/12	/12
	Balance score carried forwar	rd	/16	/16
	Total Score = Balance + Gait score	re	/28	/28

Patient stands with therapist, walks across room (+/- aids), first at usual pace, then at rapid pace.

Risk Indicators:

Tinetti Tool Score	Risk of Falls
≤18	High
19-23	Moderate
≥24	Low

